In the proportional odds model we assume that the relationship between each level in the outcome variable is proportional, so the effect that describes the relationship between the lowest category versus all higher categories of the outcome variable is the same as the relationship that describes the next lowest category and all higher categories. The proportionality assumptions will be explored graphically e.g. the logit of the empirical cumulative distribution function of the outcome should be parallel among categories of covariate X_j , and a partially proportional odds model may be pursued. The covariates that will be included in the model are those listed in the descriptive analyses, which include the important variable of baseline severity. Duplication of comorbidity variables will be avoided; only the Elixhauser score will be used. To check other model assumptions, the approaches described in Regression Modeling Strategies (Harrell 2015, 2nd ed.) will be used, i.e. we will assess the model fits, residual plots, partial effect plots, and/or anova plots (Wald minus the d.f.) will be displayed. Model results will be summarized with point estimates, 95% C.I., and p-values displayed in tabular form or graphically, along with model fit statistics.

Secondary Analysis

We have specified a single primary endpoint, and so we are not adjusting for multiplicity. Since our secondary endpoint should be more sensitive than the primary for changes in the outcomes, we are not employing a gatekeeping strategy. We will proceed with the secondary analysis regardless. With up to 5 outcome measurements per patient, a proportional odds model will be specified to include the random effect of patient and we will include number of days since enrollment. We will additionally include the time by treatment interaction to determine whether there is a differential treatment effect of proning over the observational window.

For exploratory outcomes, binary outcomes will be modeled assuming a logit link function, and ordinal and discrete outcomes will be modeled using a proportional odds model. Similar approaches will be used to modeling as for the main analyses.

Missingness

We do not expect missingness on our primary outcome. There may be missingness on covariates or on secondary or exploratory outcomes. We will not exclude cases with missing covariates. We will use multiple imputation with predicted mean matching. Cases with missing outcomes may also have the outcomes imputed

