Subgroup analyses and differential treatment effects

To determine whether effects of treatment depend on any of the baseline characteristics, we will test the interaction between the characteristic and treatment effect in the PO model. Only if it is significant will we conduct a separate subgroup analysis. In this case, we will be liberal when considering whether a potential effect modifier has an interaction with the treatment, using a p-value of <0.2 . For continuous variables, of which age is the primary variable of interest, we will not create artificial groups but instead we will present the partial effect plots demonstrating how the treatment effect changes over age. If warranted, a subgroup analysis may be conducted using the same model as for the primary outcome, but with the subgroup-defining variable removed from the model. We will not adjust subgroup analyses for multiplicity, but all data reports will clearly indicate the potential for false positive findings. We will focus these subgroup analyses on estimates of potential group specific effects rather than significance testing. Any findings will be subject to further confirmatory studies. Subgroup analyses will be performed using the intention to treat sample.

Summary

The analyses described here are those necessary to answer the trial's primary question of whether advising patients to prone is more effective than usual care in improving clinical status five days after being hospitalized for Covid-19 with requirements for supplemental oxygen. Beyond our analysis exploring the effect of treatment on primary, secondary, and exploratory endpoints, we expect there to be multiple additional exploratory analyses conducted, in particular as they relate to the supplementary study and understanding the association between objective measures of proning and moment-to-moment oxygen levels. It is not possible to predetermine the nature of such analyses. However, we are committed to preserving rigor and reproducibility and will pre-specify each subsequent analysis in the context of the specific question to be answered, cognizant of bias and missingness in the data.

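### For small categorical subgroups, the SAP's optional refit of the full covariate model is less precise, and its intervals cover less well, than the interaction model the plan already fits

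*SAP*

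**What the plan says.** The SAP section on subgroup analyses starts from the full sample: "we will test the interaction between the characteristic and treatment effect in the PO model". A subgroup analysis follows conditionally: "Only if it is significant will we conduct a separate subgroup analysis", with significance judged liberally, "using a p-value of <0.2". The stated method is optional: "a subgroup analysis may be conducted using the same model as for the primary outcome, but with the subgroup-defining variable removed from the model". A variable drops out in this way when it is constant in the sample being fitted, so the natural reading is a separate fit inside each level.

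The primary model is defined under Main Analysis: "The covariates that will be included in the model are those listed in the descriptive analyses". For comorbidity, "only the Elixhauser score will be used". That leaves age, sex, BMI, race, ethnicity, Elixhauser score, smoking, renal replacement therapy, vasopressors and baseline oxygen device.

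Continuous modifiers are handled differently: "we will not create artificial groups but instead we will present the partial effect plots". On purpose, the SAP states: "We will focus these subgroup analyses on estimates of potential group specific effects rather than significance testing". It sets no minimum subgroup size, no reduced covariate list and no penalisation for the subgroup fits.

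**The concern.** A covariate list chosen for about 550 patients may be carried unchanged into a subgroup a tenth of that size. A proportional odds model fitted by maximum likelihood with few patients per coefficient tends to push estimates away from the null and to give Wald intervals that are too narrow. In very small levels it may not converge. Because continuous variables are not cut, the subgroups are levels of categorical variables, and some of these could be small: minority race categories, renal replacement therapy, vasopressors, non-invasive ventilation at enrollment.

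The plan intends to present these results as estimates, so bias and interval coverage matter more here than the test. The interaction model already fitted to screen the modifier contains the same subgroup-specific ORs and estimates the covariate effects from everyone.

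**Working it through.** **1. The plan's own figure.** The documents give no subgroup-level figure. The whole-trial one is N=500 for OR 1.6 at 80% power (protocol section 8). Whitehead's formula, 1:1 allocation, two-sided 5% (assumed):

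N = 12(1.960+0.842)² / [(ln 1.6)² × (1 − Σp̄³)] = 94.19 / [0.2209 × (1 − Σp̄³)] = 426.4 / (1 − Σp̄³)

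- Protocol day-5 distribution as listed: Σp̄³ ≈ 0.1195, so N = 426.4/0.8805 = 484.
- Granular scale with 50% on room air (10% + 40%): the treated share is 1.6/2.6 = 0.615, the mean is 0.558 and its cube 0.173, so N = 426.4/0.827 = 516.

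These lie either side of 500, so the granular outcome simulated below is compatible with the plan.

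**2. Model size (coding assumed).** Age 1, BMI 1, Elixhauser 1, sex 1, device 2, race 4, ethnicity 2, smoking 3, renal replacement 1, vasopressors 1: total 17, plus arm = 18 slopes. With race, ethnicity and smoking reduced to two levels each: 17 − 3 − 1 − 2 = 11. Patients per slope at 17 df: 550/18 = 31 in the full sample, 50/18 = 2.8 in a subgroup of 50.

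**3. Subgroup sizes (assumed).** A level holding 10-20% of 550 has 55-110 patients. The range examined was 30 to 250.

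**4. Simulation before the p<0.2 screen.** True OR 1.6, about 17 covariate df, 2,000 trials per cell, Wald 95% CI. The contrast comes from one model on 550 patients with shared covariate effects.

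| Subgroup n | Refit coverage | Refit OR (exp of mean log OR) | Contrast coverage | Contrast OR |
|---|---|---|---|---|
| 40 | 84.1% | 2.59 | - | - |
| 50 | 85.8% | 2.14 | 94.1% | 1.64 |
| 60 | 89.0% | 1.95 | - | - |
| 80 | 90.8% | 1.85 | - | - |
| 100 | 91.6% | 1.78 | 94.8% | 1.64 |
| 150 | 93.1% | 1.70 | 94.3% | 1.63 |
| 250 | 94.2% | 1.66 | - | - |

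About 13% of refits did not converge at n=30, 7% at 50 and 1% at 100. Every contrast fit converged. A smaller set of contrast runs (1,000 trials per cell, n from 30 to 250, OR 1.6 and 1.0) gave 92.9-95.6%.

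At true OR 1.0 the refit shows no material mean bias, but coverage is 87.0%, 91.5% and 93.2% at n=50, 100 and 150.

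Precision with 15 covariate df, SD of the log OR, refit vs contrast: 1.03 vs 0.58 at n=50 and 0.45 vs 0.38 at n=110. The variance ratios are (1.03/0.58)² = 3.2 and (0.45/0.38)² = 1.4.

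**5. Sensitivity of refit coverage at n=50, 100, 150 (true OR 1.6).** Half the prognostic strength: 87.6%, 91.1%, 92.5%. About 11 covariate df: 90.3%, 93.8%, 92.7%. Only 5 df (device, age, BMI, Elixhauser): 92.3%, 94.8%, 94.8%.

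**6. After the p<0.2 screen, no true interaction.** For a small subgroup the interaction statistic is driven mainly by that subgroup's own error. Nearly all of the 5% of intervals that miss therefore fall among the 20% of results that pass: 5/20 = 25% missing, or about 75% coverage even for a well-calibrated method. Simulated ranges over OR 1 and an effect of size 1.6 (several sets of runs, about 15-16 df):

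| Subgroup n | Contrast | Refit |
|---|---|---|
| 40 | 68-75% | 66-70% |
| 50 | 69-78% | 60-65% |
| 80 | 68-76% | 65-67% |
| 110 | 75-83% | 70-74% |
| 250 (OR 0.625 only) | 85% | 86% |

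Median absolute error of the log OR after the screen, at OR 0.625 (= 1/1.6), contrast vs refit: 1.07 vs 1.73 at n=40 and 0.59 vs 0.66 at n=110.

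**The case against.** The strongest reply is that the p<0.2 screen, not the refit, causes most of the coverage loss in what would be reported. When there is no true interaction this is right (step 6), and the change proposed here leaves the screen in place. A reader might infer from step 4 that switching to the contrast restores 94-95% coverage. It does not for screened results: the gain there is a few points up to roughly a dozen, plus smaller error in the estimate.

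A reader might also infer that the plan will estimate every subgroup effect by refitting and uses the interaction model only for a test. The text supports neither. The refit is optional and conditional, and for continuous modifiers, with age named as the main one, the plan already presents the effect from the interaction model. The point reaches categorical modifiers only.

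The size of the problem depends on inputs the documents do not give: the baseline mix, the covariate coding and the prognostic strength. With a leaner coding much of it goes by n=100.

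Finally, these analyses are exploratory. The SAP promises a false-positive warning and defers to confirmatory studies, and the primary result is untouched. That limits the consequence, but the warning concerns multiplicity. It does not tell a reader that an OR is inflated or an interval too short.

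**Conclusion.** The point holds as a cheap improvement to an optional analysis. For small categorical subgroups the permitted refit is less precise than a model the plan already fits. Before selection its 95% CI covers about 84-90% at 40-60 patients and 91-94% at 100-150, against about 94-96% for the contrast. The OR is exaggerated when a true effect exists, and not materially biased on average at OR 1. At 250 patients the refit covers 94.2%, so a subgroup variable such as sex, if reasonably balanced, is little affected. After the p<0.2 screen both methods under-cover, roughly 68-83% for the contrast and 60-74% for the refit at 40-110 patients with no true interaction.

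These figures assume 550 patients, 11-17 covariate df, about half the patients on room air at day 5, and subgroup sizes that the documents do not state.

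**What to change.** Replace the SAP sentence that permits the refit with: *For categorical modifiers, subgroup-specific ORs and 95% CIs will be obtained as contrasts from the treatment-by-subgroup interaction model fitted to the full intention-to-treat sample, in place of separate within-subgroup models.* Add that intervals reported after the p<0.2 screen do not have nominal 95% coverage.

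The cost is a few lines of SAP text. It needs no new data and one fewer set of models. The statistical price is that covariate effects are assumed common across subgroup levels. Whether to keep the p<0.2 screen is a separate decision that this change does not settle.
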